FRIEDRICH-ALEXANDER
UNIVERSITÄT
ERLANGEN-NÜRNBERG

Department of Sport Science and Sport
Friedrich-Alexander-University Erlangen Nürnberg

Facilitating Motor Skill Learning by Aerobic Training in Parkinson's Disease II FaST-PD II

Study Protocol

FaST - PD

Facilitating Motor Skill Learning by
Aerobic Training in Parkinson's Disease

Universitätsklinikum
Erlangen
Molekulare Neurologie
Ambulanz für Bewegungsstörungen

Krankenhaus
Rummelsberg

Akademisches Lehrkrankenhaus der
Friedrich-Alexander-Universität Erlangen-Nürnberg

Contact

Principal Investigator:

Dr. phil. [name]

Affiliation: Department of Sport Science and Sport,
Friedrich-Alexander University Erlangen-Nürnberg

[contact]

E-Mail: [contact]

Sub-investigator:

[name]

Affiliation: Department of Sport Science and Sport,
Friedrich-Alexander University Erlangen-Nürnberg

[contact]

E-Mail: [contact]

Collaborators

Department of Molecular Neurology, Faculty of Medicine, University Erlangen-Nürnberg ([name]. med. [name], [name]. med. [name])

Klinik für Neurologie, Krankenhaus Rummelsberg (PD Dr. med. [name])

Funding

Deutsche Stiftung Neurologie (DSN)

Summary

The study is designed to assess the effects of cardiovascular (aerobic) exercise on motor skill learning in Parkinson patients. Specifically, the investigators examine whether a single bout of moderate-intense aerobic exercise, performed immediately following motor skill practice, facilitates motor memory consolidation. In this experimental trial, participants will be randomly allocated to either an intervention group (motor skill practice + aerobic exercise) or control group (motor skill practice + seated rest).

Background

Parkinson's disease (PD) is a progressive neurodegenerative disorder that is characterized by motor control impairments, such as gait disturbances and postural instability. Beneficial effects of exercise are attributed to mechanisms of neuroplasticity, and task-specific motor training (repeated practice of a skill) is consequently considered to be a motor learning process. Importantly, the formation (acquisition) and consolidation of motor memories is impaired in PD compared to healthy individuals of similar age.

Thus, it is crucial to identify strategies to enhance motor learning in people with PD. Recent studies have accumulated evidence to show that acute (single bouts of) cardiovascular exercise can facilitate motor skill learning. However, this evidence is mainly derived from studying healthy individuals. In a first study including PD patients, we recently found improved motor memory consolidation, but not skill acquisition, when practice was preceded by a single bout of cardiovascular exercise.

These results suggest that acute exercise may enhance motor memory formation processes, but could potentially interfere with motor skill acquisition when performed prior to practice. Consequently, the present study investigates whether performing a single bout of cardiovascular exercise immediately following skill practice will enhance motor memory consolidation without affecting skill acquisition in PD.

Aims/Hypothesis

The main question of the study is whether a single bout of moderate-intense aerobic exercise, performed immediately following motor skill practice, facilitates motor memory consolidation in Parkinson Disease.

Hypothesis:

1. An acute cardiovascular exercise bout performed immediately following skill practice leads to increased motor skill consolidation (larger offline gains) after 24 h and 7 days.

Outcome measures

Motor skill learning

A dynamic balance task will be used to assess participants' motor learning performance. The device consists of a 107 x 65 cm wooden platform (stability platform; Lafayette Instrument Europe; Loughborough, United Kingdom), which is mounted on a fulcrum and has a maximum deviation of 15° to either side. Participants are required to stand with both feet on the platform and try to keep the platform as close to the horizontal as possible during a 30 seconds trial. A millisecond timer measures angular displacement from horizontal during each 30 seconds trial. Participants will be secured with a safety harness and instructed to stand in a comfortable position.

Primary outcome measure – Precision

Description: Time in balance (angular displacement $\pm 5^\circ$ from horizontal) during each 30 seconds trial.

Secondary outcome measure – Variability:

Description: Root mean square error (average angular deviation from horizontal) during each 30 seconds trial.

Memory consolidation (offline learning):

To assess motor skill consolidation (offline learning) primary and secondary outcomes will be calculated as change scores from the final performance (last practice block) during skill practice to skill performance in a 24-hour and 7-day retention test, respectively (Figure 1).

Study design

In an experimental trial, participants will be randomly allocated to one of two groups (Figure 1). Each experimental arm includes i) a pre-examination 2 - 14 days before ii) an acquisition session where the motor skill will be practiced, followed by a retention test iii) 24 \pm 2 hours and iv) 7 days later (Figure 1). On acquisition day, the experimental group will perform a single bout of aerobic exercise (cycle ergometer) immediately following motor practice, whereas the control group will rest.

Conditions:

- 1. Experimental condition:** Participants in the experimental group will practice the ***motor learning task*** followed by a single bout of moderate-intensity ***aerobic exercise*** on a cycle ergometer during acquisition day.
- 2. Control condition:** Participants in the control group will practice the ***motor learning task*** followed by a ***seated rest*** period during acquisition day.

[figure not shown]

Fig. 1 Study design.

Aerobic exercise bout:

The acute cardiovascular exercise bout comprises a 5-minutes warm-up (intensity will be progressively increased until target intensity), followed by 25 minutes of pedaling at 60–80 rpm and 60% of maximal power output reached in a graded exercise test during pre-examination.

Rest:

The resting phase includes seated rest on a chair for 30 minutes. Participants will be permitted to read during the 30 minutes.

Motor skill practice:

Irrespective of group allocation, participants will follow the identical skill practice routine. On acquisition day, participants will perform a familiarization trial followed by 15 practice trials (30 seconds), clustered into 5 blocks of 3 trials, with 60 seconds rest between trials and 120 sec rest between blocks. 24 hours as well as 7 days later, participants will perform a retention test consisting of one familiarization trial (to account for potential warm-up effects) and one practice block (3 trials) on the stability platform, respectively.

Study population

Inclusion criteria:

Patients are eligible if they have

- a Hoehn and Yahr score of ≤ 3 ;
- a score of ≤ 1 in the UPDRS item 'postural instability';
- are able to stand and walk independently; and
- are not familiar with the motor task.

Exclusion criteria:

Criteria for exclusion are

- higher level of cognitive impairment indicated by a score of <21 in the Montreal Cognitive Assessment (MoCA);
- other clinically relevant neurological, internal or orthopedic conditions besides Parkinsonism that would interfere with the exercise paradigm or motor learning task;
- (musculoskeletal conditions or surgery 1 year before the study enrolment;
- smoking>10 cigarettes/day or drinking>6 cups of coffee/day or >50 g of alcohol (equivalent of two glasses of wine) consumption/day (Winter et al., 2007).

Statistical analysis plan

Power calculation:

Considering data from similar previous experiments, an a priori estimation of the required sample size for the primary analysis was performed using the statistics program G*Power (version 3.1.9.2). Accordingly, to identify a significant interaction effect for offline learning (change from end of skill acquisition to 24h/7-day retention test) with large effect sizes ($f=0.58$; according to previous studies) with a statistical power of 80% and a significance level of $p\leq.05$, 26 subjects ($n=13$ per group) need to be included.

Statistical analysis:

The effect of aerobic exercise on motor skill learning will be examined by separate mixed ANOVAs testing for the between-subject factor Condition (aerobic exercise, rest) and the within-subject factor Blocks. Two separate ANOVAs will be performed for 24-hour and 7-day retention, respectively. Specifically, effects of aerobic exercise on offline learning will be analyzed in a 2 (aerobic exercise, rest) x 2 (last practice block during acquisition, first block during 24-hour/ 7-day retention test) model.

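### Does the missing rule for turning three trial values into one block score undermine the analysis of time in balance and RMSE?

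*Combined protocol and SAP*

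**What the plan says.** Under Outcome measures, both outcomes are tied to one trial. The primary is "Time in balance (angular displacement $\pm 5^\circ$ from horizontal) during each 30 seconds trial". The secondary, headed as variability, is given as "Description: Root mean square error (average angular deviation from horizontal) during each 30 seconds trial".

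The paragraph on memory consolidation moves to the block: "primary and secondary outcomes will be calculated as change scores from the final performance (last practice block) during skill practice to skill performance" at each retention test. Under Motor skill practice, the acquisition trials are "clustered into 5 blocks of 3 trials", and each retention test has a familiarization trial and then "one practice block (3 trials) on the stability platform". Under Statistical analysis, the two levels of the within-subject factor are "last practice block during acquisition, first block during 24-hour/ 7-day retention test".

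Each participant therefore supplies three trial values for every cell of the 2 x 2 model. The readable text does not say how they are combined, and it gives no rule for a block with a missing trial. The consolidation paragraph points to Figure 1, which is not reproduced in the copy reviewed. Its caption names only the study design.

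**The concern.** The block score is the dependent variable of every planned test: both outcomes, at 24 hours and at 7 days. Several scores fit the wording: the mean, the median, the best trial or, for RMSE, one root mean square taken over all 90 seconds. They can differ noticeably within one participant. If the rule were chosen after the data were seen, the analyst could pick the one that gives significance, and the 5% error rate would no longer hold. With 13 participants per group, a few borderline change scores can decide the result. A noisier score, such as the best trial, could also seem to put the planned 80% power at risk.

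**Working it through.** **1. The plan's own figure.** Inputs from the Power calculation section: f = 0.58, alpha 0.05, power 80%, 26 participants (13 per group). In a 2 x 2 mixed design, the interaction test is equivalent to comparing the two groups' change scores. With d = 2f = 1.16, the noncentrality is f² x N on 1 and N - 2 degrees of freedom.

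- N = 24: 0.3364 x 24 = 8.07, power 0.775.
- N = 26: 0.3364 x 26 = 8.75, power 0.810.

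So 26 is the smallest balanced total that reaches 80%. The calculation uses only f, and the plan does not say which block score f came from.

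**2. How far the scores can differ.** Take illustrative trial RMSEs of 4, 6 and 9 degrees (assumed values):

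- mean: 19/3 = 6.33
- pooled: square root of (16 + 36 + 81)/3 = 6.66
- median: 6.00
- best: 4.00

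**3. Time in balance.** Pooling over the block gives the total time in balance over 90 seconds, which is three times the mean. Multiplying every score by 3 leaves the F statistic unchanged, so the two whole-block readings of the primary outcome are the same test.

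**4. Why the mean is the default.** Suppose all trials are entered, with trial as a further within-subject factor. With complete data, the condition-by-block interaction is tested against block-by-subject variation. Both terms are built from averages over trials, so the F is the one obtained from block means. An analyst who averages first and one who enters every trial reach the same planned test.

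**5. Simulation for RMSE.** The documents give no variances, so these are assumptions: between-subject SD 1.5 degrees, session SD 0.4-1.0, trial-to-trial SD 0.5-1.5, and d = 1.16 assigned to the change in the mean of three trials. There were 40,000 studies per setting, with 13 per group. Ranges are over the nine settings.

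| Block score | Power | Significance verdict differs from the mean |
|---|---|---|
| Mean | 80-81% | - |
| Pooled | 79-81% | 0.4-3.5% |
| Median | 71-80% | 4-15% |
| Best trial | 61-79% | 6-24% |

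With no true effect, the most favourable of all four rules gives 7.0-10.5% false positives per test. The more favourable of mean and best gives 6.2-7.9%. A repeat with 20,000 studies per setting agreed to within about one percentage point; its upper limit for mean against pooled was 3.8%. In a further run of 20,000 per setting, the more favourable of mean and pooled gave 5.1-5.7%.

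**The case for a change.** The strongest case for a change is that an expected convention is not a written rule. Nothing in the text stops a choice made after seeing the data. The undefined quantity is the dependent variable of the main test, and one sentence would close the gap without any new measurement. RMSE has an extra ambiguity, since mean and pooled scores differ. Its gloss as an average deviation could also suggest a mean absolute deviation.

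Part of this stands. The rule is not written, and a reader cannot confirm from this document that it was fixed in advance. The rest is weaker than it looks:

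- **Power.** The lower figures for median and best trial arise only because f = 0.58 was assigned to the mean of three. Had f come from best-trial scores, power under best-trial scoring would be about 81% by construction. The sample size was also set for the primary analysis, whereas the simulation is of RMSE.
- **Primary outcome.** No simulated figure covers time in balance, which is bounded at 0-30 seconds. The four-rule false-positive range cannot be carried over, since two of the four rules coincide there.
- **Which rules are plausible.** The consolidation paragraph scores performance in a block, and the ANOVA factor is blocks. Nothing points to a best trial or a median, and these two produce the large numbers.
- **Familiarization trial.** Motor skill practice already separates it from the practice trials and the retention block and gives its purpose, so its exclusion follows.
- **RMSE wording.** Root mean square error about horizontal fixes the formula within a trial. The variability heading and the bracketed gloss are loose wording that would not alter the calculation.

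**Conclusion.** The observation is accurate: outcomes are defined per trial and analysed per block, with no stated combining rule. It is missing detail rather than an error in the plan. The mean of the three trials is the evident reading, and an analyst following the plan would use it. The tests would then be sound as planned. The 26 participants and the stated 80% power are unaffected, because the plan's effect size is given without a scoring rule.

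For RMSE, the remaining choice between mean and pooled scoring changes the significance verdict in roughly 0.4-4% of simulated studies and leaves the false-positive rate close to nominal, at 5.1-5.7% even if the better of the two is reported. The 7.0-10.5% range is a worst case: it applies to RMSE only, under assumed variances, and requires all four rules to be tried and the best one reported. A block with a missing trial is a similar small gap, for which averaging the remaining trials is the ordinary course. Recording the mean as the block score would be a harmless courtesy to readers, but the analysis does not depend on it. The conclusion assumes that Figure 1 contains no conflicting scoring rule.

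### Does labelling root mean square error about horizontal as variability undermine the secondary outcome?

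*Combined protocol and SAP*

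**What the plan says.** All the definitions are in the combined protocol and SAP.

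- **Outcome measures, Motor skill learning.** Participants are told to "try to keep the platform as close to the horizontal as possible during a 30 seconds trial". The platform "has a maximum deviation of 15° to either side", and angular displacement is recorded "from horizontal during each 30 seconds trial".
- **Primary outcome.** Under "Primary outcome measure – Precision" it is "Time in balance (angular displacement $\pm 5^\circ$ from horizontal) during each 30 seconds trial".
- **Secondary outcome.** Under "Secondary outcome measure – Variability" it is "Root mean square error (average angular deviation from horizontal) during each 30 seconds trial". No formula is printed, no within-trial SD or mean tilt is defined, and the direction of improvement is not stated.
- **Memory consolidation (offline learning).** The "primary and secondary outcomes will be calculated as change scores from the final performance (last practice block") to the 24-hour and 7-day retention tests.
- **Aims/Hypothesis.** The single hypothesis is that exercise after practice gives larger offline gains at both times. Variability is not mentioned.
- **Statistical analysis.** Each retention time has its own 2 × 2 mixed ANOVA (condition by block: last practice block against the retention block).

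**The concern.** The heading, the named statistic and the words in parentheses do not agree. Variability normally means spread about the participant's own mean position. RMSE about horizontal is total error about a fixed target, and it grows with a steady lean as well as with fluctuation. An average deviation is a third quantity: the mean absolute deviation is smaller than RMSE whenever the size of the tilt varies, and a signed mean lets left and right tilts cancel.

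Two things would be at stake. A change in lean between practice and retention could be reported as a change in variability. And two analysts reading the same sentence might compute different numbers.

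**Working it through.** **No figure in the plan depends on this point.** The sample size concerns the primary analysis. For completeness, it reproduces as a two-group comparison of change scores with f = 0.58 and α = 0.05. With noncentrality f²N = 0.3364 × 26 = 8.75 on 1 and 24 df, power is 0.810. With N = 24 it is 0.775. So 26 is the smallest even N that reaches 80%, and nothing below alters it.

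**Inputs.** From the documents: reference position 0° (horizontal), angle range −15° to +15°, balance band ±5°, trial length 30 s. Assumed, because the documents give no tilt data: the traces below, with sine-wave oscillation. They are illustrations only.

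**Step 1: how far the three quantities can separate.** The identity is RMSE² = (mean tilt)² + SD². Each trace has RMSE 6.0°.

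| Trace | Mean tilt | SD | Mean absolute deviation | Time within ±5° |
|---|---|---|---|---|
| (a) steady lean | 6.0° | 0° | 6.0° | 0 s |
| (b) oscillation about 0° | 0° | 6.0° | 5.4° | about 12 s |
| (c) oscillation about a lean | 4.5° | √(36 − 20.25) = 3.97° | 4.8° | about 16 s |

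For (c), the amplitude is 3.97 × √2 = 5.61°. The share of time in the band is 0.5 + asin(0.5/5.61)/π = 0.53, and 0.53 × 30 s is about 16 s. The label and the gloss are therefore loose as a matter of mathematics.

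**Step 2: when RMSE and SD nearly coincide.** RMSE/SD = √(1 + r²), with r = |mean tilt|/SD.

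| r | 0.1 | 0.25 | 0.5 | 1 |
|---|---|---|---|---|
| RMSE/SD | 1.005 | 1.031 | 1.118 | 1.414 |

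The excess runs from 0.5% to 41%. The documents do not say where these patients would fall.

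**Step 3: what the planned test responds to.** The analysis uses change from the last practice block to retention.

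- Lean and SD both unchanged: RMSE does not move, so a stable group difference in lean adds nothing to the condition-by-block interaction.
- Lean unchanged, SD changed: with lean 4° and SD falling from 4.47° to 3.00°, RMSE falls from √(16 + 20) = 6.0° to √(16 + 9) = 5.0°. The direction is right, though the change is 1.0° rather than 1.47°.
- Lean changed, SD unchanged: with SD 4.47° and lean falling from 4.0° to 2.24°, RMSE falls from 6.0° to √(5 + 20) = 5.0°. This is the only one of the three cases in which the word variability would mislead. The participant is nevertheless closer to horizontal, which is a real gain on the task as instructed.

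**Step 4: is the computation ambiguous?** One statistic is named, and its reference is given. The parenthesis explains it in lay terms. A signed mean is a strained reading, since the same section uses deviation as a magnitude to either side. Taking the gloss literally as mean absolute deviation would lower the value by 10% in (b) (5.4 against 6.0) and by 20% in (c) (4.8 against 6.0). But that means setting aside the statistic actually named.

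**Step 5: does the secondary outcome merely repeat the primary?** Not in these traces. At one fixed RMSE, time in balance runs from 0 s to about 16 s.

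**Step 6: would the within-trial SD be better?** A platform resting on one 15° stop for the whole trial has RMSE 15° and SD 0°. One that spends equal time at each stop has RMSE 15° and SD 15°. With lower scored as better, SD would give the first of these the best possible score. RMSE treats both as the failures they are.

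**The case for a change.** The strongest case for a change is that outcome names travel into results tables. A reader who sees reduced variability will take it to mean steadier balance, when RMSE may have fallen only because the lean shrank. The documents give no mean tilt, so nobody can assume that RMSE and SD are close. Even with zero lean, RMSE is not an average deviation: the ratio of mean absolute deviation to RMSE is 0.798 for a normal distribution of tilt, 0.866 for a uniform one and 0.900 for a sine wave. The direction of improvement is also opposite for the two outcomes and is not written down. The repair would be a few words.

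Most of this is true as description. A fall in RMSE should not by itself be read as a fall in variability, and the gloss is imprecise. What does not stand is the consequence for the trial. The plan announces no claim about variability; it uses the measure to detect offline gains on a levelling task, where total error about horizontal is the relevant quantity. The direction follows from the task instruction, and the ANOVA F test is non-directional in any case.

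**Conclusion.** No change to the plan is needed. This is a clerical looseness in the heading and gloss of a secondary outcome. Renaming it would change no computed value, test, sample size, error rate or conclusion about offline learning. Stating that lower is better would add detail that any analyst supplies from the task. Replacing RMSE with SD would be a debatable trade, with a clear failure case at the platform stop.

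This rests on two readings: that analysts compute the statistic named (RMSE about 0°), and that results are interpreted as overall error on the task, in line with the hypothesis. The possible gap between RMSE and SD ranges from negligible (0.5% at |mean tilt|/SD of 0.1) to large (41% at a ratio of 1), and the documents do not allow it to be narrowed. That uncertainty bears on how the word variability may be used in a report, not on the validity of the planned analysis.

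### Does the 24-hour re-test spoil the 7-day comparison of offline learning?

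*Combined protocol and SAP*

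**What the plan says.** The Memory consolidation paragraph under Outcome measures scores offline learning as "change scores from the final performance (last practice block) during skill practice to skill performance in a 24-hour and 7-day retention test". Both scores share one starting point, the end of acquisition.

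Under Motor skill practice, "24 hours as well as 7 days later, participants will perform a retention test consisting of one familiarization trial" "and one practice block (3 trials) on the stability platform, respectively". The same participants attend both tests, and the arms are treated alike: "Irrespective of group allocation, participants will follow the identical skill practice routine".

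The hypothesis is that exercise after practice "leads to increased motor skill consolidation (larger offline gains) after 24 h and 7 days". For the analysis, "Two separate ANOVAs will be performed for 24-hour and 7-day retention, respectively", each a 2 x 2 model of condition by block ("last practice block during acquisition, first block during 24-hour/ 7-day retention test) model"). The Power calculation section sizes the trial on the interaction, with f = 0.58, 80% power and a 0.05 level, giving 26 participants, 13 per group.

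**The concern.** The 24-hour test lies inside the 7-day interval, and the protocol itself calls its three scored trials a practice block. The Background section says that "task-specific motor training (repeated practice of a skill) is consequently considered to be a motor learning process". On the plan's own terms, then, the 7-day change can contain learning from the 24-hour visit as well as change without practice. The familiarization trial is there for warm-up effects and does not remove such learning. The plan does not comment on the re-test, has no group tested only at day 7, and has no contrast from 24 hours to 7 days.

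Two misreadings are conceivable. A within-arm 7-day gain might be reported as purely offline. A null 7-day interaction might be taken as absent consolidation when the rest arm had in fact caught up through the 24-hour practice.

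**Working it through.** **The plan's own figure.** In a 2 x 2 mixed ANOVA, the Condition x Block interaction is the two-sample test on change scores. With f = 0.58, the noncentrality is f² x N.
- N = 24: 0.3364 x 24 = 8.07, df 1 and 22, power 77.5%.
- N = 26: 0.3364 x 26 = 8.75, df 1 and 24, power 81.0%.

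So 26 is the smallest balanced total that reaches 80%, as the plan states. On the change score, f = 0.58 is d = 2 x 0.58 = 1.16 SD.

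**Amount of re-test practice.** One familiarization trial plus three scored trials is 4, against 1 + 15 = 16 at acquisition: 4/16 = 25%. Counting scored trials only, 3/15 = 20%.

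**Where the re-test enters.** Write each arm's mean 7-day change as o + g, where o is offline change and g is the re-test gain still present at day 7.
- Interaction: (o_E − o_R) + (g_E − g_R). If g_E = g_R, the re-test drops out.
- Block effect: the average of o + g over both arms. Here g stays in.

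The documents give no SD, re-test gain or retention rate. Every g below is assumed, in SDs of the change score, with 13 per group and a two-sided 0.05 level.

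**Equal gain, no offline change.** The Block effect has 24 df and noncentrality g x √26.

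| Gain kept to day 7 | Block effect rejects | Interaction rejects with no arm difference | Interaction power at d = 1.16 |
|---|---|---|---|
| 0 | 5% | 5% | 81% |
| 0.25 SD | 23% | 5% | 81% |
| 0.50 SD | 69% | 5% | 81% |

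If only half of a 0.25 or 0.50 SD gain survives to day 7, the Block figures fall to about 9% and 23%.

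**Unequal gain.** The interaction has 24 df and noncentrality d x √(13/2).
- Rest arm catches up by a net 0.125, 0.25 or 0.50 SD: d = 1.035, 0.91 or 0.66, and power is 0.72, 0.61 or 0.37 instead of 0.81. Net means beyond what the 24-hour block mean already contains. If a block is scored as the mean of its three trials and gain is linear, net is half of total, so these cases need arm differences in practice gain of 0.25, 0.50 or 1.00 SD. The last is extreme.
- Equal consolidation, but one arm gains 0.25 or 0.50 SD more from the re-test: the 7-day interaction is significant in 9% or 23% of trials.

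**What extra estimates would add.** The 24-hour-to-7-day change equals the 7-day score minus the 24-hour score. With equal SDs and correlation r between the two scores (both assumed), the 95% half-width for its arm difference is √(2(1 − r)) x 2.064 x √(2/13), which is 0.96, 0.81 or 0.63 SD at r = 0.3, 0.5 or 0.7. That is too wide to show whether the arms gained differently.

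**The case for a change.** The strongest case for a change is that the hypothesis concerns a mechanism. Randomisation protects the total effect of exercise at day 7, but it does not make that effect a clean measure of consolidation. The mixed ANOVA will also print a Block effect, and under the plan's label an author could easily report it as offline gain. Two or three sentences fixed in advance would cost almost nothing and would keep the interpretation from being chosen after the results are known.

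The description is correct: the 7-day interval is not purely offline, and the plan does not say so. The case for a required change is weaker, for four reasons.
- The hypothesis is comparative, and the sample size rests on the interaction. The plan commits to neither of the feared readings.
- The 23% and 69% figures concern an effect that the plan does not put forward as its hypothesis test. They also assume no offline change and full retention to day 7.
- The same strictness would touch the 24-hour score, because a mean over three trials contains whatever is gained within that block. No retention measure taken by performing the task is wholly free of practice.
- A gain that differs by arm could create a positive 7-day result as well as hide one. A caution confined to nulls and within-arm gains would be one-sided, and the extra estimates could not resolve the matter in either direction.

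**Conclusion.** No change to the plan follows. The 7-day score spans a short re-test, so its within-arm change should not be called purely offline. The planned between-arm test nevertheless remains a valid test of the total effect of exercise under a schedule common to both arms. An equal re-test gain leaves its 5% error rate and 81% power intact, assuming the gain is additive. Distortion of the consolidation reading needs a gain that differs by arm. Nothing in the documents shows or excludes one, its direction is unknown, and the figures for it are hypothetical.

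The sequence of visits and the content of the re-test are stated openly in the protocol, so analysts can describe the 7-day result sensibly: change from the end of acquisition to day 7, including the 24-hour re-test. That description would apply equally to positive, null and within-arm results. It is an optional point of wording for the report and alters no test, estimate or sample size.

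### The stated 80% power holds at a retention test only if all 26 have that test's score, and the two separate ANOVAs cannot use anyone who lacks it

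*Combined protocol and SAP*

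**What the plan says.** The Power calculation section sizes the trial "to identify a significant interaction effect for offline learning (change from end of skill acquisition to 24h/7-day retention test"). It assumes f = 0.58, drawn from earlier experiments, with a power target of 80% and a 0.05 threshold, and concludes that "26 subjects ($n=13$ per group) need to be included". The figure is given as a number to include. The Statistical analysis section says that the effect of exercise "will be examined by separate mixed ANOVAs testing for the between-subject factor Condition (aerobic exercise, rest) and the within-subject factor Blocks", and that "Two separate ANOVAs will be performed for 24-hour and 7-day retention, respectively". Each is a 2 (arm) x 2 (last practice block, retention block) model.

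Under Study design, each participant has "a pre-examination 2 - 14 days before" the acquisition session, then retention tests at 24 ± 2 hours and at 7 days. The outcomes are defined as changes from the last practice block to each retention test. The document states no dropout allowance, replacement rule, missing-data method or analysis set.

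**The concern.** A power calculation returns the number of participants who must contribute data to the test. Here that number is also the number to include, and the margin above 80% is about one point. The target is therefore met only if nobody is lost from the analysis in question.

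The second issue is how a loss is handled. In a mixed ANOVA with two levels of Block, the Condition x Block interaction is the arm difference in change score. Without the retention block there is no change score, so the participant leaves that analysis. For someone who attends at 24 hours but not on day 7, the last practice block and the 24-hour score are both on file, yet neither informs the 7-day comparison. If people who did badly (or well) earlier are more likely to be absent, those left are a selected group and the 7-day contrast can be biased. With 13 per arm and no stated rule, that handling would be settled after the data are seen.

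**Working it through.** **Inputs from the Power calculation section.** f = 0.58, significance level 0.05, target power 80%, 13 per arm. Sidedness is not stated. The ANOVA F test is non-directional, so I treat it as two-sided.

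**Reproducing 26.** Treat the interaction as a two-group comparison of change scores, with d = 2f = 1.16 and d² = 1.3456. The noncentrality is λ = d² × n1 × n2 / (n1 + n2), on 1 and n1 + n2 − 2 degrees of freedom. With equal arms this is λ = f² × N.

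| Analysed at the test | λ | Power |
|---|---|---|
| 13 + 13 | 1.3456 × 169/26 = 8.746 | 81.0% |
| 13 + 12 | 1.3456 × 156/25 = 8.397 | 79.2% |
| 12 + 12 | 1.3456 × 144/24 = 8.074 | 77.5% |
| 13 + 11 | 1.3456 × 143/24 = 8.018 | 77.2% |
| 11 + 11 | 1.3456 × 121/22 = 7.401 | 73.5% |

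N = 24 falls short and N = 26 reaches 80%, so 26 is the smallest equal-group total. Other readings do not return 26. The repeated-measures setting with two measurements gives 10 at a correlation of 0.5 and 14 at 0, a normal approximation gives 24, λ = f² × (N − 2) gives 28, and a one-sided t test gives 20.

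**What a three-score model recovers.** Suppose two per arm miss day 7 only. Write r01, r02 and r12 for the correlations of last block with 24 hours, last block with day 7, and 24 hours with day 7. The documents give none of these. I assume 0.6-0.8 for r01 and r02, 0.7-0.9 for r12, equal variances and a known covariance.

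- R² of day 7 on the two earlier scores = (r02² + r12² − 2 × r01 × r02 × r12) / (1 − r01²)
- Share of the change-score variance explained by the earlier scores: q = 1 − (1 − R²) / [2(1 − r02)]
- Effective n per arm = 1 / [(1 − q)/11 + q/13]

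Taking each correlation at the low, middle and high point of its range independently, the extremes are:

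- r01/r02/r12 = 0.8/0.8/0.7: R² = (0.64 + 0.49 − 0.896)/0.36 = 0.65; q = 1 − 0.35/0.4 = 0.125; effective n = 1/(0.875/11 + 0.125/13) = 11.2; power 74.4%.
- r01/r02/r12 = 0.8/0.6/0.9: R² = (0.36 + 0.81 − 0.864)/0.36 = 0.85; q = 1 − 0.15/0.8 = 0.8125; effective n = 1/(0.1875/11 + 0.8125/13) = 12.6; power 79.6%.

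Power uses λ = d² × (effective n)/2 with 2 × (effective n) − 2 degrees of freedom. The range is thus 74.4% to 79.6%, against 73.5% for complete pairs. Estimating the covariance costs some of this. By simulation with the regression estimated from the 22 completers, 0.8/0.8/0.7 gives an effective n of about 11.0 and power of about 73.5% (no gain), and 0.7/0.7/0.8 gives about 76%.

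**Bias.** In simulations where day-7 absence was made to depend on earlier scores, with a true standardised effect of 1.16, complete pairs gave 1.22 to 1.35 and the three-score model gave 1.16. The absence mechanism is assumed, so this shows that bias can arise and be removed, not how large it would be in this trial.

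**The case against.** The strongest reply is that this is an ordinary attrition comment. If nobody is lost, 26 included does deliver the stated power. One loss costs 0.8 points below target, which is trivial beside the uncertainty in f = 0.58. The analysed pair spans only 24 hours or 7 days, so losses may be few, and no rate is documented. The two ANOVAs are separate, so missing day 7 leaves the 24-hour analysis intact. Deletion of incomplete pairs is inferred from the model, not written in the plan. All of this stands, and it limits the size of the point.

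It is also fair that the three-score model does not restore 80%, and that with complete data it changes nothing. The direct way to hold 80% is to recruit more: 26/(1 − loss rate) gives 28, 29, 31 and 33 for assumed rates of 5%, 10%, 15% and 20%. That costs patients and needs a rate the documents do not supply.

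A reader might infer that, because only one arm has an exercise bout, early stopping would make losses unequal. The documents do not support this. The last practice block is recorded before the bout, and no retention test is conditional on completing it, so stopping early removes no score. A reader might also count the whole schedule, up to three weeks, as exposure to loss. But the 2-14 days before acquisition lie outside the analysed pairs, and the document does not say whether someone lost before acquisition would count among the 26.

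**Conclusion.** The point holds as a modest one. The sample size is not miscalculated. It is the bare minimum for 26 complete pairs at each test, stated as the number to include. The shortfall is negligible with one loss, about 2.5 to 3 points below 80% with two, and 6.5 points with four (80 − 73.5), and it applies only to the test that was missed. These figures assume that f = 0.58 is the between-arm effect on change scores, the only reading tried that returns exactly 26, and a two-sided 0.05 test.

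The better reason to change the analysis is validity. The planned models cannot use scores already collected, and complete pairs can mislead if absence depends on those scores. The three-score likelihood model guards against that so long as absence depends on observed scores. It gives no such guarantee if absence depends on the unseen day-7 score. Its power gain is uncertain, from about nil to 6 points in the case worked above, and should not be sold as restoring 80%.

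**What to change.** 1. In the Power calculation section, state power by number analysed at each retention test, at f = 0.58: 26 gives 81.0%, 24 (12 + 12) gives 77.5%, 22 (11 + 11) gives 73.5%.
2. In the Statistical analysis section, replace the two ANOVAs, for each outcome, with one likelihood-based repeated-measures model of the last practice block, 24-hour and 7-day scores. Include arm, time and arm x time, with unstructured covariance and small-sample degrees of freedom. Include everyone as randomised. Read the arm contrasts in change to 24 hours and to 7 days from this model. With complete data they equal the planned interactions.

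The cost is SAP wording only, with no extra patients. The downsides are a less familiar model and a slightly less favourable power statement.
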